#### *Analysis*

The primary and secondary analyses will be conducted using only the images obtained from the R3 device in order to ensure a uniform comparison between MRI and the R3 ultrasound images with PCaVision. A comparison of the R4 images with the R3 images will be conducted to ascertain whether software modifications are necessary to guarantee that PCaVision can be utilised with the R4 ultrasound system. The measured CEUS signal, SWE metrics and B-Mode will be compared. To validate the comparable output signals of R3 and R4, 50 patients will be required to undergo an additional R4 ultrasound scan.

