### 6.1.2 PCaVision quality control

PCaVision is using automated detection of ultrasound image quality by measuring parameters of CEUS and patient motion. Patients will not be processed by PCaVision if they do not fulfil these criteria. Loose criteria are default and used for the primary outcome. A combination of stricter criteria is used for additional (secondary outcome) diagnostic accuracy analysis.

Quality parameter	Specification	Loose	Strict
CEUS signal	Minimum peak intensity value (dB)	43	50
Patient motion	Minimum IoU (intersection over union) of B-mode prostate contours	0.60	0.70
	Maximum root mean square magnitude of detected motion vectors (mm)	8.1	3.0

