## **Appendix I**

### *Comparative analysis of the LOGIQ E10 R3 and LOGIQ E10 R4 ultrasound machines*

#### *Rationale*

This study compares the PCa detection rate based on MRI with that of ultrasound using PCaVision. PCaVision has been developed based on ultrasound images created with a GE LOGIQ E10 ultrasound device, version R3. A more recent iteration of the device (GE Logic E10, version R4) is available for use in patient care. To ensure that PCaVision operates safely with the input from this newer ultrasound device (R4), an in-patient comparison with both devices is necessary. New study patients who are willing to participate in the current study will be asked to undergo an additional scan with both devices.

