#### *Procedure*

The procedure will be fully explained to the patient during the informed consent consultation. The patient will undergo two 10-minute scans in a single session. The ultrasound scans will be performed using a probe that is inserted transrectally only once. First, the R3 scan will be conducted, then the probe will be disconnected from the R3 device and connected to the R4 device. This way, the probe does not need to be reinserted in the rectum of the patient. In both scans, a bolus of contrast fluid (SonoVue) will be administered. There are no adverse effects associated with administering a second bolus, and it is described as safe by the manufacturer. The total procedure will take approximately 10 minutes longer than usual.

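### The R3/R4 sub-study is justified by PCaVision working safely on R4 scans but compares only the software's inputs; running PCaVision on both recordings would answer the stated question at little cost

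*Combined protocol and SAP*

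**What the plan says.** Appendix I, Rationale, explains why the second scan is needed: "To ensure that PCaVision operates safely with the input from this newer ultrasound device (R4), an in-patient comparison with both devices is necessary". Its Analysis paragraph gives a narrower purpose, namely "to ascertain whether software modifications are necessary to guarantee that PCaVision can be utilised with the R4 ultrasound system", then names the variables: "The measured CEUS signal, SWE metrics and B-Mode will be compared". The number is stated without derivation: "To validate the comparable output signals of R3 and R4, 50 patients will be required to undergo an additional R4 ultrasound scan".

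The Procedure paragraph fixes the order: "First, the R3 scan will be conducted, then the probe will be disconnected from the R3 device and connected to the R4 device". It also says: "In both scans, a bolus of contrast fluid (SonoVue) will be administered". The R4 recording therefore always follows a second bolus in the same session.

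The sub-study is kept apart from the main trial: "The primary and secondary analyses will be conducted using only the images obtained from the R3 device".

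Section 6.1.2 sets an automated quality check with fixed limits on CEUS peak intensity (43 dB loose, 50 dB strict), overlap of B-mode contours (0.60, 0.70) and motion (8.1 mm, 3.0 mm). Its consequence is: "Patients will not be processed by PCaVision if they do not fulfil these criteria".

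**The concern.** The reason given to the men and to the ethics committee concerns how PCaVision behaves on R4 scans. The planned comparison concerns what R4 feeds into PCaVision. Two sets of inputs can look alike on average while a classifier gives different maps. Inputs can also shift while every result stays the same. Nothing in Appendix I says that PCaVision will be run on the R4 recordings, or that any of its results will be set against the R3 result in the same man.

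A second, separate weakness is the fixed order. A difference between the recordings could come from the device, the second bolus, residual contrast or the later scan. Appendix I does not acknowledge this.

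At stake is the sub-study's own conclusion. It could report that the devices are comparable, or that the software needs changing, without knowing whether PCaVision's result changed in any of the 50 men.

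**Working it through.** **1. Inputs or results?** Section 8.3.2 (Ad 3) describes separate analyses of B-mode, CEUS and SWE that end in a classifier parametric map. The three items compared in Appendix I are therefore on the input side. PCaVision's own results are the quality-check pass or fail (6.1.2), the classifier map (8.3.2), and the support it gives the physician on lesion presence and position (6.1.1). Appendix I lists none of these. The output signals it mentions are those of the two ultrasound machines.

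**2. What the signal comparison can deliver at n = 50.** The figure of 50 cannot be reproduced, because no margin, standard deviation, agreement target, alpha or power is given. In units of the SD of the paired difference:

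- Half-width of the 95% CI for the mean difference: t(0.975, 49)/√50 = 2.010/7.071 = 0.28 SD.
- Half-width for each limit of agreement: 2.010 × √(1/50 + 1.96²/(2×49)) = 2.010 × √0.0592 = 0.49 SD.

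These are usable precisions, but without an acceptance limit neither leads to a decision. The quality check shows why. A given fall in CEUS peak intensity changes the result for a man just above 43 dB and changes nothing on that criterion for a man well above 50 dB. The mean shift does not say how many men are of each kind.

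**3. Order.** With R3 always first, the paired difference is

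R4 − R3 = device effect + order effect.

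The device and order columns of the design matrix are identical (rank 1 of 2), so the two effects cannot be separated at any sample size.

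**4. What a per-man comparison of results would deliver.** The exact (Clopper-Pearson) 95% limits for k agreements in n pairs are Beta⁻¹(0.025; k, n−k+1) and Beta⁻¹(0.975; k+1, n−k):

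| Agree / pairs | Agreement | Exact 95% CI |
|---|---|---|
| 50/50 | 100% | 92.9% to 100% |
| 48/50 | 96% | 86.3% to 99.5% |
| 45/50 | 90% | 78.2% to 96.7% |
| 40/50 | 80% | 66.3% to 90.0% |
| 36/40 | 90% | 76.3% to 97.2% |

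The last row allows for lost pairs. Section 4.5 plans 438 men to obtain 350 evaluable, and 350/438 = 0.80. If the same share applied here (an assumption, since that allowance covers both imaging techniques and biopsy problems), 0.80 × 50 = 40 pairs would remain.

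**5. Limit of 50 as a pass/fail test.** As an illustration only, showing agreement above 80% at one-sided 2.5% needs at least 46 of 50 (exact alpha 1.8%). Power is 43% if true agreement is 90%, and 90% if it is 95%. The comparison is best read as an estimate with an interval.

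**The case against.** The strongest reply is that the analysis fits the purpose given in its own paragraph. PCaVision was developed on R3 images, and asking whether R4 delivers similar inputs is the natural first compatibility check. It also touches the quality check, whose limits are set on CEUS intensity and B-mode contours. This stands. A reader might infer that the sub-study measures nothing relevant, and the documents do not support that. What remains is that the Rationale promises more than this comparison can show. Narrowing the Rationale would also remove the mismatch, but it would leave the more useful question unanswered with the recordings already in hand.

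Other tempting inferences also fail:

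- *That the fixed order is a mistake to be reversed.* Scanning R3 first means that the recording used in the main analyses is never preceded by another bolus. The documents do not give this as the reason, but it is a real advantage. The size of any order effect is not in the documents.
- *That lesion agreement comes free from the software.* Under section 5.1 a urologist reads the PCaVision images and marks lesions, so this would need a second, blinded human reading.
- *That correcting the R4 CEUS signal for its pre-contrast level would remove the order problem.* That would treat the devices unequally and depart from the absolute dB limits in 6.1.2. Section 8.3.2 describes a recording made after contrast is given and does not establish a baseline.
- *That comparing results removes the confounding.* It does not. With no repeat R3 scan, disagreement still mixes device, order and scan repeatability.

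**Conclusion.** The point holds as a minor, inexpensive improvement to Appendix I. The planned comparison covers PCaVision's inputs. With no tolerance linking a signal difference to a changed result, it cannot show whether PCaVision gives the same result in the same man on R4. Independently, a difference between recordings cannot be assigned to the device.

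A reader might infer that the trial's non-inferiority result or its biopsy decisions are at risk. The documents do not support this. The main analyses are restricted to R3 images, and nothing says that R4 images guide biopsies. No stated figure is contradicted.

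The gain from the change is a per-man agreement estimate with a 95% interval roughly 19 to 21 percentage points wide at 90% observed agreement (96.7 − 78.2 = 18.5 with 50 pairs; 97.2 − 76.3 = 20.9 with 40). This rests on both recordings being stored in a form that PCaVision 1.0 can process and, for the smaller figure, on the assumed 20% loss of pairs.

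**What to change.** In Appendix I, Analysis, add that:

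- The same locked PCaVision 1.0 is run off-line on both recordings of each sub-study man.
- Per-man agreement on quality-check pass or fail is reported at the loose and the strict limits of section 6.1.2, with exact 95% CIs.
- Agreement of the classifier map is reported among men passing on both devices, using a measure chosen before the R4 results are seen.
- The denominator is the number of usable pairs for each comparison, not automatically 50.
- The CEUS, SWE and B-mode comparison is kept to explain any disagreement, with no correction applied to R4 alone.
- A difference cannot be attributed to the device alone, because order, second bolus and scan repeatability are not separated.
- R4 output is not used to select biopsy targets.

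Keep R3 first so that the main analysis is untouched. Agreement on lesion presence and location is optional. If it is added, a urologist should read the R4 maps blinded to R3, and that reading time is an extra cost.

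The core change needs no additional man, scan or bolus. It costs a few sentences and a small amount of analyst time.
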